## 9.6 Investigators' Responsibility to Report Serious Adverse Events/Serious Adverse Device Effects

Investigators must immediately report all SAEs/SADEs on the SAE Report Form which has been integrated in the eCRF - irrespective of expectedness or relationship to study procedures or study devices.

For reported deaths, the Investigator should provide any additional information, as requested and required, such as autopsy reports or terminal medical reports.

The Investigator should complete and (electronically) sign the form, and send it (electronically, within the eCRF system) to:

- **Study Safety Officer:** [name]

In case, the eCRF system is not functioning, a paper version of the form should be completed by hand, signed and sent as described above (faxed or e-mailed).

If SAE/SADE information is unsatisfactory and essential data is missing, the Investigator is requested to conduct the necessary follow-up actions and/or to provide additional information as soon as possible.

## 9.7 Sponsor's Responsibility to Report Serious Adverse Events/Serious Adverse Device Effects

The below **Study Safety Officer** is responsible for all safety related topics of the study:

Name:

[REDACTED]

E-mail:

[REDACTED]

Phone:

[REDACTED]

Fax:

[REDACTED]

Upon receipt of an SAE Report Form, the Study Safety Officer will:

- Review the SAE Report Form for completeness and make a medical assessment.
- Ensure that additional (initially, follow-up and final) information is obtained and communicated, as applicable.

After Safety Assessment the SAE/SADE is reported, as applicable, via the following internal lines:

Roche Q-Function is responsible for reporting of initial, follow-up and final SAE reports to:

- Regulatory Authorities.

Study Manager or designee is responsible for reporting to:

- Ethics Committees
- Other Investigators

## 10 Malfunction and Incidents

The CE-marked medical devices observed in this study are used within the Intended Use.

The documentation and reporting of the incidents and indirect harms will follow the guidance provided in Medical Devices (MEDDEV) 2.12.-1 rev. 8 (January 2013) and local regulations and guidelines.

### 10.1 Definitions

#### 10.1.1 Definition of Device Deficiency

A device deficiency is any inadequacy of a medical device with respect to its identity, quality, durability, reliability, safety or performance.

NOTE Device deficiencies include malfunctions, use errors and inadequate labelling.

#### 10.1.2 Definition of Malfunction

A malfunction is a failure of a study device to perform in accordance with its intended purpose by users, operators or other users without any medical impact on subject.

#### 10.1.3 Definition of Incidents

An incident is any malfunction or deterioration in the characteristics and/or performance of a device, as well as any inadequacy in the labelling or the instructions for use which, directly or indirectly, might lead to or might have led to the death of a subject, or user or of other persons or to a serious deterioration in their state of health.

An indirect harm may occur as a consequence of the medical decision, action taken/not taken on the basis of information or result(s) provided by the device. Examples include:

- Misdiagnosis
- Delayed diagnosis
- Delayed treatment
- Inappropriate treatment

### 10.2 Incident Reporting

The Investigators should identify incidents with direct and indirect harms of devices with CE-mark used within Intended Use (as defined in the beginning of this section), and report such on the **Incidents Report** (integrated into the eCRF) which should be sent to the Sponsor immediately.

Even if the requested information is not yet complete, it is required to submit the report immediately.

Respective contact details can be found in the Investigator site file and in the Incident Report in the eCRF.

Subjects will report such incidents to the respective Call Centre, as usual for these products or inform their Investigator. Contact details will be noted on subject's identification card.

In case of doubt on the duty to report an incident, there should be a pre-disposition to report rather than not to report - as a general principle

Incidents with devices from other manufacturers should be reported directly to the respective manufacturer.

CONFIDENTIAL

Identified malfunctions will be submitted to the Sponsor – either via the eCRF or by means of a separate **Malfunction Report**.

In addition, all incidents and indirect harms are also to be documented in the source data. The following details should be provided:

- Description of event/incident
- Start date
- Resolution date
- Action taken
- Outcome

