### 3.3 Status of Documentation of Study Device(s)

The Accu-Chek® Solo micropump system will not have CE marking when the study starts. A manufacturer’s declaration will be provided. CE marking is expected to be available before the end of the study. On availability of CE mark, CE marked material will be usable in the study and will be handed out to the study subjects as appropriate. As the differences to the non-CE marked material are minor (mainly bug fixes), the effects on study outcomes are negligible.

All other devices have CE marking and marketed in countries of the European Union.

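### Immediate incident reporting covers only CE-marked devices, so before its CE mark a harmless near miss with Solo reaches the sponsor only by a route with no deadline, except possibly in Germany

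*Protocol*

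**What the plan says.** Protocol section 10.2 defines what goes on the Incidents Report: "The Investigators should identify incidents with direct and indirect harms of devices with CE-mark used within Intended Use". That report goes to the sponsor at once: "Even if the requested information is not yet complete, it is required to submit the report immediately". For its scope, 10.2 points back to the opening of Section 10, which also speaks only of marked devices: "The CE-marked medical devices observed in this study are used within the Intended Use".

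Section 3.3 gives the status of the investigational device: "The Accu-Chek® Solo micropump system will not have CE marking when the study starts". It adds: "CE marking is expected to be available before the end of the study". No date is given. Table 1 lists all five Solo components as unmarked at study start and every other study device as marked.

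The definition of an incident in 10.1.3 is not restricted by CE status. It includes failures that "might lead to or might have led to the death of a subject" or to serious deterioration in health. A malfunction (10.1.2) is a failure of any study device "without any medical impact on subject". Section 10.2 sends malfunctions to the sponsor through the eCRF or a separate form and states no time limit.

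**The concern.** The definition and the reporting rule do not match. By definition, an incident includes a dangerous failure that happened to do no harm, whichever device failed. The rule that makes reporting immediate is limited to marked devices, and the one system outside that limit is the system under investigation.

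What is at stake is how soon the sponsor learns of a hazard. Solo delivers insulin, and section 8.1 lists hypoglycemia, and hyperglycemia that may progress to ketoacidosis, among the risks of pump therapy. Section 2.2 says the study starts before CE marking partly so that the product can be optimized, and section 3.3 describes the later marked material as differing mainly by bug fixes. This is the period in which early notice of a near miss would do most to protect other subjects.

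**Working it through.** No sample size, power or event rate bears on this point. The check compares the reporting rules and then applies simple arithmetic to delay and exposure.

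**Which rule catches a harmless but potentially dangerous failure of an unmarked Solo?**

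| Route | Where | Covers unmarked Solo? | Covers a near miss? | Immediate? |
|---|---|---|---|---|
| Incidents Report | 10 (opening), 10.2 | No | By definition 10.1.3, yes; by the wording of 10.2, unclear | Yes |
| SAE/SADE, general definitions | 9.1.2, 9.1.4, 9.6 | Yes | No, a serious consequence must have occurred | Yes |
| SAE, German definition | 9.1.2, 9.6 | Yes | Yes, if there was an untoward medical event | Yes |
| Malfunction report | 10.1.2, 10.2 | Yes | Yes | No time limit stated |
| Device deficiency | 10.1.1 | Yes | Yes | Defined, but no reporting rule uses the term |

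The study countries are Austria, Germany, Poland and the UK. In three of the four, only the malfunction row remains. In Germany the third row may help. A purely technical failure without any medical event may still fall outside it.

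The second row of doubt is in 10.2 itself. Its operative sentence speaks of incidents with direct and indirect harms, which can be read as requiring harm. On that reading, removing the CE restriction would not be enough to bring near misses in.

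**How late could the notice be?** Malfunctions and incidents are recorded at Visits 3, 4 and 5 (sections 7.4 to 7.6), and section 7.13 has sites enter data during or shortly after visits. Suppose a malfunction is first recorded at the next scheduled visit:

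- nominal gap: 13 weeks × 7 = 91 days;
- Visit 2 to Visit 3, with the later visit at the end of its window: 91 + 14 = 105 days;
- Visit 3 to 4 or Visit 4 to 5, with the windows at opposite ends: 91 + 14 + 14 = 119 days.

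These are upper bounds. They assume no Call Center contact, unscheduled visit or interim eCRF entry.

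**How much Solo use is there?** The inputs are 60 subjects per group (section 11.1) and the group schedules in section 2.1.

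- Group A: 60 × 39/52 = 45 patient-years.
- Groups B and C after week 26: 120 × 13/52 = 30 patient-years.
- Total: 45 + 30 = 75 patient-years.

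This is a ceiling at nominal visit times. It assumes full enrolment, no drop-out (section 11.1 allows for up to 18%) and no CE mark during the study, and it includes German sites. The documents give neither the CE date nor the split by country, so the affected part cannot be calculated. They give no failure rate either.

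**The case against.** The strongest reply is that the protocol runs two tracks. Section 9, based on ISO 14155, covers the investigational device, and Section 10 adds vigilance for marketed devices. Solo failures are not left without a route:

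- malfunctions of any study device go to the sponsor;
- subjects receive a Call Center card at Visits 2 and 4;
- incidents are recorded at Visits 3 to 5 without a CE limit;
- hyperglycemia suspected to come from leakage or occlusion is a captured AE (section 9.3.1.1);
- 10.2 tells sites to report when in doubt;
- Section 10 and section 12.1 cite local regulations and ISO 14155, which may demand more.

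Much of this stands. It shows that what is missing is a stated deadline, not a route. It does not supply the deadline: none of the routes that reach a harmless near miss of an unmarked Solo is timed outside Germany. The cited external texts cannot be consulted here, so the point concerns the protocol text alone.

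Three stronger readings are tempting and are not supported:

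- A reader might infer that Solo near misses have no immediate route anywhere. The German SAE definition, with the immediate rule in 9.6, contradicts that.
- A reader might infer that the same fault in OmniPod must be reported to the sponsor at once. Section 10.2 sends incidents with other manufacturers' devices directly to the manufacturer and attaches no time limit to that sentence, so the contrast cannot be drawn.
- A reader might call Solo the least-tested device. The documents say only that it is the one system without a mark, and section 2.2 states that essential requirements are met.

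**Conclusion.** The point holds within these limits. As written, immediate incident reporting omits only the investigational system, and only until it is marked. During that time, a Solo failure that could have caused death or serious deterioration but did no harm is covered only by the untimed malfunction route. Germany is a possible exception where an untoward medical event occurred. Solo failures with serious harm are reported immediately in all four countries.

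The 75 patient-years should not be read as the size of the gap. They are the most Solo use the design can produce on its nominal schedule, and the gap is an unknown fraction of that. The delay of up to 119 days is likewise a worst case. The issue is a correctable mismatch in a safety rule. It does not affect the primary analysis, and it should be corrected because the change is cheap and concerns prompt notice of hazards.

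**What to change.** In section 10.2, apply the immediate Incidents Report to all study devices irrespective of CE mark. Three further edits are needed for this to work:

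- align the scope sentence that opens Section 10, because 10.2 refers back to it and would otherwise bring the limit back in;
- replace or clarify the wording on direct and indirect harms, so that near misses as defined in 10.1.3 are expressly reportable;
- reconcile the rule with the sentence on other manufacturers' devices, so that sites know whether an OmniPod incident also goes to the sponsor, and when.

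Alternatively, keep Section 10.2 for marked devices and add an immediate-reporting rule for device deficiencies (10.1.1) of the investigational device that could have led to serious harm. This uses a term already defined and applies the same standard in all four countries.

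The cost is protocol wording, eCRF help text, a site notice and a few more immediate reports. The form already exists. If conduct is complete, the sponsor can instead check the malfunction reports for unmarked Solo devices against the incident definition in 10.1.3. The SAP (section 6.12) only tabulates and lists defective devices by type and arm, so it would not show which failures were potentially serious.

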## 11 Statistical Considerations and Data Analysis

The primary and secondary analysis as defined in this study protocol will be described in the Statistical Analysis Plan (SAP) and summarized in the final Clinical Study Report (CSR). All additional exploratory analyses required for publications or requested for different needs will be included in a separate Appendix e.g. Publication Analysis Plan (PAP). This might include any ad-hoc additional analyses not defined in the final version of the study protocol/amendment and the SAP.

### 11.1 Null Hypotheses and Sample Size Calculation

Assessment of treatment satisfaction in patients with type 1 diabetes comparing standard therapy via MDI to patch pumps.

First Null hypothesis: There is no difference in treatment satisfaction between Accu-Chek® Solo and MDI.

First Alternative hypothesis: Treatment satisfaction is higher with Accu-Chek® Solo than with MDI.

Second Null hypothesis: There is no difference in treatment satisfaction between Accu-Chek® Solo and mylife™ OmniPod.

Second Alternative hypothesis: Treatment satisfaction is higher with Accu-Chek® Solo than with mylife™ OmniPod.

The first and second Null hypothesis are tested using a hierarchical procedure. Only if the first Null hypothesis of no difference in treatment satisfaction between Accu-Chek® Solo and MDI can be rejected, the second Null hypothesis of no difference in treatment satisfaction between Accu-Chek® Solo and mylife™ OmniPod will also be tested.

Sample size calculation is based on the expected difference and variability in the DTQ change score between the Accu-Chek® Solo and the MDI group. An anticipated mean score of 90 in the MDI group and of 110 in the Solo group and a standard deviation of 30 is used for sample size calculation.

A sample size of 49 subjects per group will have a 90% power to detect a significant difference at a two sided alpha level of 0.05. To adjust for a maximum drop-out rate of up to 18%, 60 subjects will be enrolled in every treatment arm.

To allow for comparison between the Accu-Chek® Solo and the mylife™ OmniPod, the same number of subjects as in groups A and B will be enrolled in group C. No assumptions on the difference in change of treatment satisfaction between the Accu-Chek® Solo and in the mylife™ OmniPod groups are made and thus, sample size is not adjusted for this comparison. Also, since testing of the first and the second Null hypothesis will be performed using a hierarchical procedure, no multiplicity correction and thus no sample size adjustment is necessary.

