## Protocol Outline

For comprehensive details, please refer to the respective sections.

Study Title:	Patient-Reported Outcomes with the Accu-Chek® Solo Micropump System vs. Multiple Daily Injection Therapy vs. mylife OmniPod® in People with Type 1 Diabetes
Short Name	PRO Solo Study
Investigational Device:	Accu-Chek® Solo micropump system
Other Study Devices:	
 
- Intensified therapy with multiple daily injections (MDI)
 
- mylife™ OmniPod® Insulin Management System (Insulet Corporation)
 

Research Question/ Working Hypothesis:	
Assessment of treatment satisfaction in patients with type 1 diabetes comparing Accu-Chek® Solo to standard therapy via MDI and to mylife™ OmniPod®.
 
First Null hypothesis: There is no difference in treatment satisfaction between Accu-Chek® Solo and MDI.
 
First Alternative hypothesis: Treatment satisfaction is higher with Accu-Chek® Solo than with MDI.
 
Second Null hypothesis: There is no difference in treatment satisfaction between Accu-Chek® Solo and mylife™ OmniPod®.
 
Second Alternative hypothesis: Treatment satisfaction is higher with Accu-Chek® Solo than with mylife™ OmniPod®.

Primary Objective:	To compare treatment satisfaction with Accu-Chek® Solo versus MDI and versus mylife™ OmniPod® assessed by Diabetes Technology Questionnaire (DTQ).
Secondary Objectives:	
To evaluate
 
 
• Mean HbA1c change difference between treatment groups at end of study
 
• Therapy relevant examination and diary parameters
 
• The answers of additional questionnaires measuring psychological parameters relevant in diabetes therapy
 
• Therapy relevant parameters from data download from BG-meter or respective patch pump, e.g. bolus frequency
 
• Device parameters
 

Indication	Type 1 diabetes mellitus
Target Population	Age ≥ 18 years
Number of Subjects	180 subjects, 60 subjects in each treatment group
Number of Sites	10-20
Countries	Austria, Germany, Poland, and UK
Study Design:	
Prospective, multinational study where adults ≥ 18 years will be randomly allocated (1:1:1 ratio) to
 
Group A: Continuous subcutaneous insulin infusion (CSII) with Accu-Chek® Solo micropump system for 26 weeks.
 
or

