### 2.1 Study Design Overview

This is a multinational randomized, three arm interventional study. Subjects will be randomized to one of the following treatments:

- **Group A:** Accu-Chek® Solo micropump system for 39 weeks
- **Group B:** MDI for 26 weeks, then Accu-Chek® Solo micropump system for 13 weeks
- **Group C:** mylife™ OmniPod® for 26 weeks, then Accu-Chek® Solo micropump system for 13 weeks

Total duration is 40 weeks, during which all subjects switch from MDI to tubeless CSII at a time point determined by their allocated group. After 26 weeks, all subjects will use Accu-Chek® Solo micropump system.

In the case that mylife™ OmniPod® should not be commercially available in a country; no subjects will be randomized into Group C at the respective sites.

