- A 3-arm study design has been chosen where two tubeless pump systems are compared with the standard therapy (MDI). This maximizes information gain while minimizing subjects numbers.
- HbA1c was not chosen as the primary objective. Instead the primary objective is a measure of device satisfaction. The main reason for this is the fact that therapy adherence strongly influences therapy success. Thus, factors that are suitable to improve therapy adherence over a long time may predict clinical outcome concerning complications even better than HbA1c.
- In order to provide comparability with other studies, HbA1c has been kept as secondary objective.
- Finally, in order to minimize effects of subject's or investigator's preferences, subjects will be randomly allocated to their treatment group (A, B or C respectively A or B\*). (\*at sites in countries where mylife™ OmniPod® is not commercially available)

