#### **3.2.2 mylife™ OmniPod® Insulin Management System**

The mylife™ OmniPod® Insulin Management System is a patch pump system designed by Insulet Corporation. It was first brought to the US market and is available worldwide (including UK and Germany) since 2010 under the brand name mylife™ OmniPod®.

[figure not shown]

Figure 6: mylife™ OmniPod® Pod (left top), mylife™ OmniPod® infusion set (left bottom) and mylife™ OmniPod® Personal Diabetes Manager (right)

The mylife™ OmniPod® Insulin Management System is comprised of two components: the actual Pod and a Personal Diabetes Manager (PDM) that serves as remote control of the pod.

The Pod is single-use disposable, microprocessor-controlled infusion pump that is worn directly on the body. The adhesive on the base of the Pod keeps it in place for the typical wear times of 48 to 72 hours.

The PDM is a hand-held, battery-powered device integrating a blood glucose (BG) meter that remotely controls the insulin delivery of the pod. BG and insulin therapy data are stored and can be displayed directly on the PDM. In addition, the PDM provides further information on audio alarms, alerts, and reminders related to insulin delivery, reservoir level, Pod functioning, and battery life.

The Pod incorporates an insulin reservoir holding up to 2 ml (i.e. 200 units of U100 insulin) which has to be filled by the user with equipment provided with each Pod (fill syringe and needle). A separate infusion set or reservoir is not needed. Insulin is delivered through a soft cannula integrated in the Pod and inserted automatically into the subcutaneous tissue at an angle of 45°.

All components of the mylife™ OmniPod® diabetes management system used in the study will have CE marking.

Subjects in group C will use this device for 26 weeks.

This device has been chosen as comparator, as it is the only patch pump available on the market so far and therefore defines the class of patch pumps.

For the time of mylife™ OmniPod® use during the study, the Sponsor will cover the costs for the mylife™ OmniPod® Insulin Management System.

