## 2.2. Study Design

This study is conducted as a prospective, multinational, multicenter, three-arm study where adults with type 1 diabetes will be enrolled in approximately 20 sites.

A total of 180 subjects will be randomly allocated in a 1:1:1 ratio to the three treatment groups.

Due to the character of the used devices, no blinding procedure will be utilized.

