#### **6.8.1.1. DTQ**

For DTQ both the change scores and the status scores will be analyzed. For the change scores, the same ANCOVA as for the primary analysis will be used. All other comparisons will be analyzed using t-tests.

Difference scores as described in section 6.8.1 will be performed both on the “now” scores and on the “change” scores, even though the latter ones already reflect differences/changes.

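### Equal groups of 60 are stated without condition, but the OmniPod country rule would shrink group C and leave Solo–OmniPod comparisons that lack a site term open to country differences

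*Protocol*

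**What the plan says.** The Protocol Outline states that subjects "will be randomly allocated (1:1:1 ratio) to" the three groups, with 60 in each. Protocol 11.1 derives 60 per arm from the Solo–MDI comparison and then says that "the same number of subjects as in groups A and B will be enrolled in group C". SAP 2.2 is equally unconditional: "A total of 180 subjects will be randomly allocated in a 1:1:1 ratio to the three treatment groups". SAP 2.8 repeats the 60 per arm.

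Protocol 2.1 sets a different rule for any country where OmniPod is not commercially available: "no subjects will be randomized into Group C at the respective sites". Protocol 2.2 restates it as allocation to A or B only "at sites in countries where mylife™ OmniPod® is not commercially available". The SAP does not mention this exception.

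The participating countries are Austria, Germany, Poland and the UK. On availability, Protocol 3.2.2 says that OmniPod "is available worldwide (including UK and Germany) since 2010". Austria and Poland are not addressed there.

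On analysis, SAP 6.6 fits the primary DTQ comparison with site as a covariate. SAP 6.8.1.1 uses the same model for DTQ change scores, and SAP 6.8.1.2 also adjusts HbA1c for site. For the rest of the DTQ, SAP 6.8.1.1 says: "All other comparisons will be analyzed using t-tests". SAP 6.11 compares withdrawal between arms with a Fisher test. The by-arm tables have no site restriction.

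**The concern.** Two rules in the plan cannot both hold as written once a single country lacks OmniPod. With the total fixed at 180 and 1:1:1 kept at the remaining sites, every subject at a two-arm site goes to A or B, and group C cannot reach the size of the other two. The protocol gives equal size as what makes the Solo–OmniPod comparison possible, and that comparison is the second confirmatory hypothesis.

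The second issue is comparability. Randomisation balances A against C only within sites that offered both. If part of group A comes from countries where nobody could receive OmniPod, an A–C comparison that ignores site sets different mixes of countries against each other. Questionnaire scores and withdrawal may well differ by country, so a country difference could be read as a device difference.

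**Working it through.** **1. The plan's own figures.** Inputs from Protocol 11.1 are means of 110 and 90 (difference 20), SD 30, two-sided alpha 0.05, power 90% and drop-out 18%. The normal approximation gives 48 per group. The exact t calculation gives 49, with power 90.4%. Then 49/(1−0.18) = 59.8, rounded up to 60. The stated 49 and 60 reproduce.

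**2. Group sizes under the country rule.** Let s be the share of the 180 subjects at A-or-B-only sites, with 1:1 allocation there and 1:1:1 elsewhere.

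- C = 180(1−s)/3 = 60(1−s)
- A = B = 180[(1−s)/3 + s/2] = 60 + 30s
- Group A subjects at two-arm sites = 90s
- Share of A at two-arm sites = 90s/(60+30s)

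The documents do not give s, so the values below are assumptions. The last column assumes that mean scores at two-arm sites differ by 10 points from those elsewhere. It shows the resulting shift in an unadjusted A–C difference, which is the share of A times 10.

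| s | C | A = B | Share of A with no OmniPod arm at site | Shift (points) |
|---|---|---|---|---|
| 0 | 60 | 60 | 0% | 0 |
| 10% | 54 | 63 | 9/63 = 14% | 1.4 |
| 25% | 45 | 67.5 | 22.5/67.5 = 33% | 3.3 |
| 40% | 36 | 72 | 36/72 = 50% | 5.0 |

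**3. What would restore 60 in group C.** Keeping 1:1:1 at three-arm sites needs a total of 180/(1−s), which is 200, 240 or 300 for s = 10%, 25% or 40%. Alternatively, the ratio at three-arm sites could change. At s = 25%, two-arm sites hold 45 subjects (22.5 each in A and B), and allocating the other 135 as 37.5/37.5/60 gives 60 per group. The plan describes neither.

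**4. Effect on precision.** This step takes 82% evaluable, SD 30 and, for illustration only, a 20-point difference. For s = 0, 10%, 25%, 40%:

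- Solo–OmniPod, joint three-arm model with a site term (normal approximation): 91%, 89%, 85%, 78%.
- Solo–OmniPod, three-arm sites only (t-test): 90.5%, 87%, 81%, 71%.
- Solo–MDI, joint model (normal approximation): 91%, 92%, 94%, 95%.

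**5. Which analyses are exposed.** The DTQ change-score and HbA1c ANCOVAs contain site, so a difference between sites does not pass into the A–C estimate. Solo versus MDI is available at every site. What remains is any Solo–OmniPod comparison of DTQ status or difference scores by t-test, the Fisher test on withdrawal, and the by-arm tables.

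**The case against.** The strongest reply is that the shortfall is hypothetical. Protocol 2.1 words the exception conditionally, and no document says that a participating country lacks OmniPod. A reader might infer from Protocol 3.2.2 that Austria and Poland had none, but the two named countries are given as examples of worldwide availability, not as a complete list. Table 1 of the protocol footnotes country exceptions for blood glucose meters and lancing devices and has none for OmniPod. SAP version 1.2, written in the final phase of the study, still says 1:1:1. This stands: the documents do not show that group C fell short. They do not exclude it either, since the SAP never mentions the exception.

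A reader might also infer that the second hypothesis loses its planned power, for instance 71% instead of 90% at s = 40%. The documents do not support that. They set no power target for Solo versus OmniPod and make no assumption about its difference; the 20 points belongs to Solo versus MDI. The lower series also results from discarding the two-arm sites. In a joint model with site, those sites inform A–C indirectly through MDI: at s = 25% they cut the variance by about 8%.

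Third, the exposure to confounding is limited. Some of the t-tests are within-arm comparisons of Visit 4 with Visit 5, V1–V4 differences remove stable country offsets, and the tables are descriptive. This stands too, and it keeps the point modest. Status scores at a single visit and withdrawal have no such protection, and Protocol 11.6 foresees pairwise Solo–OmniPod tests on secondary parameters.

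**Conclusion.** The point holds in conditional form. The unqualified 1:1:1 and 60 per arm conflict with the country rule, and neither document reconciles them. If two-arm sites exist and the others keep 1:1:1, group C falls below 60 in proportion to their share, and between a seventh and a half of group A would have no OmniPod counterpart at the same site for shares of 10% to 40%.

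The possible bias is confined to Solo–OmniPod comparisons without a site term. Its size rests on two assumptions that the documents do not supply, the share and the country difference. The 3.3 points at 25% is therefore an illustration, not an estimate. The powered Solo–MDI comparison is not harmed, and the confirmatory Solo–OmniPod test is already protected by its site covariate. The change is worth making because it is cheap and removes an avoidable bias.

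**What to change.** 1. In Protocol 11.1 and SAP 2.2 and 2.8, state which countries, if any, randomise to A or B only, and give the resulting expected group sizes in place of an unconditional 60 per arm. If there are none, say so; the point then closes.
2. Keep the second confirmatory hypothesis as the site-adjusted ANCOVA on the full analysis set. Restricting it to three-arm sites would depart from the all-randomised population and lose some information.
3. For between-arm DTQ comparisons now assigned to t-tests, use a model with site and baseline. For the Fisher test and the by-arm Solo–OmniPod tables, stratify by site or show the comparison for sites that randomised to all three arms. With 180 subjects at about 20 sites (180/20 = 9 per site), the restricted display is probably the more practical choice for withdrawal.

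The cost is a few sentences, one site-level flag and a little more analysis work. Any restricted table has fewer Solo subjects: at s = 25%, 45 enrolled instead of 67.5.
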